# **PROTOCOL SYNOPSIS**

Sponsor: BioMed Valley Discoveries, Inc.	Investigational Product: BVD-523	Developmental Phase: Phase 1/2
Title of Study: Phase 1/2 Dose-Escalation, Safety, Clir ERK1/2 Inhibitor BVD-523 in Patients	nical Activity, Pharmacokinetic and with Acute Myelogenous Leukem	d Pharmacodynamic Study of the ia or Myelodysplastic Syndromes
Protocol Number: BVD-523-02		
Indication: Acute Myelogenous Leukemia (AML)	or Myelodysplastic Syndrome (MI	DS)

 
Objectives: Primary objectives:
 
To define the safety and tolera dose-limiting toxicities (DLT) Dose (RP2D).
 
To determine the pharmacokin or MDS.
 
	bility of BVD-523 in patients with , the maximum tolerated dose (MT netic profile of BVD-523 and selec	AML or MDS by determining the D), and the recommended Phase 2 ted metabolites in patients with AML
Secondary objectives:		
To assess clinical response in p     Phase 2 Dose (RP2D).	patients with AML or MDS treated	1 with BVD-523 at the recommended
• To determine the progression-free survival (PFS) and duration of response (DOR) of AML or MDS patients treated with BVD-523 achieving CR (complete remission)/CRp (complete remission with incomplete platelet recovery).		
Exploratory objective:		
• To evaluate pharmacodynamic	e marker (biomarker) measures.	
Methodology/Study Design: BVD-523-02 is an open-label, multicen expansion phase (Part 2).	tter, Phase 1/2 study with a dose-es	scalation phase (Part 1) and a cohort
Part 1 – Dose-escalation Phase: A class maximum tolerated dose (MTD), and the treatment cohort will be assigned to rece schedule (b.i.d.) for 21 days (a "Cycle" doses of BVD-523 until disease progress withdrawal criterion is noted. Treatment necessary to manage adverse events. A doses will not be escalated unless the pro- 21 days (1 cycle).	sic "3+3" design will be used to es ne recommended Phase 2 dose (RP eive sequentially higher oral doses ), starting at a dose of 300 mg. Pat ssion, unacceptable toxicity, or a cl nt cycles will occur consecutively 	tablish dose limiting toxicities (DLT), (2D). Three to six patients per s of BVD-523 on a twice daily tients will receive twice-daily oral linical observation satisfying another without interruption, except when e based on Cycle 1 safety data and at dose have been observed for at least
of a single drug-related DLT in one of these 3 patients will prompt enrollment of up to 3 additional patients to that same cohort. When more than 1 DLT occurs in $\leq 6$ patients in a dosing cohort, dose escalation will be stopped and this dose level will be identified as the non-tolerated dose. Doses between the non-tolerated dose		

and the preceding lower dose, where  $\leq 1$  DLT occurred, may be explored to more precisely define the MTD. This strategy allows for a rigorous determination of MTD, especially if the dose increase that resulted in determination of the non-tolerated dose is relatively large (i.e., > 50%).

During the study, the Sponsor and Investigators may request that cohorts be enlarged or that evaluation of intermediate doses between 2 planned escalation steps be explored. Such requests will be discussed with the Investigator(s), Sponsor and Medical Monitor, and should be based on all data existing at that time, including

Sponsor:	Investigational Product:	Developmental Phase:
BioMed Valley Discoveries, Inc.	BVD-523	Phase 1/2

safety and clinical activity, determinations of pharmacokinetics, pharmacodynamics, and cumulative toxicity. Before each escalation, investigators will be consulted to ensure that all involved agree with the escalation decision.

Part 2 – Cohort-expansion Phase: Additional patients will be recruited to one of two groups - Group 1: RAS mutant positive AML or MDS; Group 2: RAS mutant negative AML or MDS - to receive treatment at the Recommended Phase 2 Dose (RP2D). Patients will receive twice daily oral doses of BVD-523 in 21-day treatment cycles until disease progression, unacceptable toxicity, or another withdrawal criterion is met. Treatment cycles will occur consecutively without interruption except when necessary to manage adverse events.

#### **Study Population- Criteria for Inclusion:**

Patients eligible for inclusion in this trial must fulfill all of the following criteria:

- 1. Provide signed and dated informed consent prior to initiation of any study-related procedures that are not considered Standard of Care (SOC).
- 2. Male or female patients aged  $\geq$  18 years.
- 3. Have either of the following diagnoses:
  - a. Morphologically confirmed AML (except acute promyelocytic leukemia (APL)) including leukemia secondary to prior therapy (e.g., chemotherapy, radiation therapy (XRT)) or antecedent hematologic disorder (e.g., MDS or myeloproliferative disorders), who have failed to achieve CR or who have relapsed after prior therapy and are not candidates for potentially curative therapy.
  - b. Intermediate-2 or High-grade risk MDS (including chronic myelomonocytic leukemia (CMML)).
- 4. Have received at least one prior therapy. Patients who are over age 65 and have not received therapy for AML are also eligible, if they are not candidates for induction chemotherapy.
- 5. Eastern Cooperative Oncology Group (ECOG) performance status of 0 (fully active, able to carry out all pre-disease activities without restriction) to 2 (ambulatory and capable of all self-care but unable to carry out any work activities; up and about more than 50% of waking hours), measured within 72 hours before the start of treatment.
- 6. Predicted life expectancy of  $\geq$  3 months.
- 7. Adequate renal function [creatinine  $\leq 1.5$  times ULN (upper limit of normal)] or glomerular filtration rate (GFR) of  $\geq 50$ mL/min.
- 8. Adequate hepatic function [total bilirubin  $\le 1.5 \text{ x UNL}$ ; AST (aspartate transaminase) or ALT (alanine transaminase)  $\le 3 \text{ x UNL}$  or  $\le 5 \text{ x UNL}$  if due to liver involvement by tumor].
- Adequate cardiac function, ≥ institutional lower limit of normal e.g., left ventricular ejection fraction (LVEF) of ≥ 50% as assessed by multi-gated acquisition (MUGA) or ultrasound/echocardiography (ECHO); corrected QT interval (QTc) < 470 ms.

- 10. Contraception:
  - For women: Negative pregnancy test for females of child-bearing potential; must be surgically sterile, postmenopausal (defined as no menstrual cycle for at least 12 consecutive months), or compliant with an acceptable contraceptive regimen (oral contraceptives, condom with spermicide, etc.) during and for 3 months after the treatment period. Abstinence is not considered an adequate contraceptive regimen.
  - For men: Must be surgically sterile, or compliant with a contraceptive regimen (as above) during and for a minimum of 3 months after the treatment period.
- 11. Willing and able to participate in the trial and comply with all trial requirements.
- 12. For Part 2 Group 1 of the Study ONLY:

Positive for RAS mutation at a Clinical Laboratory Improvement Amendments (CLIA)-certified laboratory prior to study entry.

Spor BioN	isor: 1ed Valley Discoveries, Inc.	Investigational Product: BVD-523	Developmental Phase: Phase 1/2		
Crite Patie	Criteria for Exclusion: Patients who fulfill one or more of the following criteria will not be eligible for inclusion in this trial:				
	Concomitant malignancies except prostate cancer treated with prostate complete surgical excision more the nore than 8 years ago.	carcinoma in situ, basal or squamo tectomy more than 10 years ago; ea nan 5 years ago; carcinoma in situ o	bus cell skin carcinoma; low grade arly stage melanoma treated with of cervix treated with cone procedure		
2. 0 1 5	Gastrointestinal (GI) condition that history of GI surgery, may be enro study medication. Refractory naus to enrolling such a patient.	t could impair absorption of study lled after discussion with the medi sea and vomiting must also be disc	medication (specific cases e.g., remote cal monitor), or inability to ingest ussed with the Medical Monitor prior		
3. 1	Uncontrolled or severe intercurren	t medical condition.			
4.	Patients with rapidly increasing pe blast count with white blood cell ( on hydroxyurea will be excluded.	ripheral blood blast counts (signifi WBC) > 30,000) or uncontrolled (a	cant increase in the absolute peripheral absolute blast count $> 30,000$ ) while		
5. ]	Known uncontrolled central nervor either untreated or being treated withere is evidence that the CSF cell	us system (CNS) involvement. (St ith a stable dose (or doses) of intra count is decreased and that patient	Table asymptomatic CNS involvement -thecal therapy(ies) can be allowed if is responding to IT therapy.)		
6.	Any cancer-directed therapy (chen etc.) within 28 days or 5 half-lives	notherapy, radiotherapy, hormonal, (whichever is shorter).	therapy, biologic or immunotherapy,		
7. 1 1	Any concurrent or prior use of an i lives (whichever is shorter) prior to termination of the investigational of related toxicity except alopecia sho	nvestigational drug (including ME o the first dose of BVD-523. A mi drug and administration of BVD-52 ould have recovered to Grade 1 or	X inhibitors) within 28 days or 5 half- nimum of 10 days between 23 is required. In addition, any drug- less.		
8. ] 1	Received chemotherapy regimens nitrosourea or mitomycin C). Rece with limited potential for delayed t	with delayed toxicity within the lase eived chemotherapy regimens give toxicity within the last two weeks.	st four weeks (six weeks for prior en continuously or on a weekly basis		
9.	Ongoing anticoagulant therapy tha who require anticoagulant therapy should not be considered for this st	t cannot be held if necessary to per and cannot be maintained on low r tudy.	rmit bone marrow sampling. Patients molecular weight heparin (LMWH)		
10.1	Major surgery within 4 weeks prio	r to first dose.			
11.1	Pregnant or breast-feeding women				
12.	Any evidence of serious active infe enrollment and on active treatment	ections (subjects who have been fe t would not be considered excluded	ver-free for 24 hours prior to 1).		
13. i	Any important medical illness or a in this study (based on the investig	bnormal laboratory finding that we ator's judgment).	ould increase the risk of participating		
14.	A history or current evidence/risk	of retinal vein occlusion (RVO) or	central serous retinopathy (CSR).		
15.	Concurrent therapy with drugs knows strong inducers of CYP3A4 (for list	own to be strong inhibitors of CYP st of non-permitted drugs, see App	1A2, CYP2D6, and CYP3A4, or endix 1).		
Test	Product, Dose and Mode of Adn	ninistration:			
Part 21 da subje reduc (whie	Part 1: BVD-523, starting at an oral dose of 300 mg taken with at least 8 ounces of water twice-daily for each 21 day cycle, with escalating dose levels (classic 3+3 design). Dosing of each subject will continue until the subject withdraws from the study or dies. A subject that has a Dose Limiting Toxicity (DLT) may be dose reduced or be withdrawn from the study depending upon the decision of the Safety Monitoring Committee (which includes the Sponsor, Medical Monitor and the study investigator) in Part 1.				
Part	2: BVD-523, recommended Phase	2 dose (RP2D), taken orally with	at least 8 ounces of water twice-daily		

Sponsor:	Investigational Product:	Developmental Phase:
BioMed Valley Discoveries, Inc.	BVD-523	Phase 1/2

for each 21 day cycle. Dosing of each subject may continue until the subject is discontinued from the study. A subject that has a Dose Limiting Toxicity (DLT) may be dose reduced or be withdrawn from the study depending upon the decision of the Safety Monitoring Committee (which includes the Sponsor, Medical Monitor and the study investigator).

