## 4.3 INCLUSION CRITERIA

Patients eligible for inclusion in this trial must fulfill all of the following criteria:

- 1. Provide signed and dated informed consent prior to initiation of any study-related procedures that are not considered Standard of Care (SOC).
- 2. Male or female patients aged  $\geq$  18 years.
- 3. Have either of the following diagnoses:
  - Morphologically confirmed AML (except acute promyelocytic leukemia (APL)) including leukemia secondary to prior therapy (e.g., chemotherapy, XRT) or antecedent hematologic disorder (e.g., MDS or myeloproliferative disorders), who have failed to achieve complete remission (CR) or who have relapsed after prior therapy and are not candidates for potentially curative therapy.
  - Intermediate-2 or High-grade risk MDS (including chronic myelomonocytic leukemia (CMML)).
- 4. Have received at least one prior therapy. Patients who are over age 65 and have not received therapy for AML are also eligible, if they are not candidates for induction chemotherapy.
- 5. ECOG performance status of 0 (fully active, able to carry out all pre-disease activities without restriction) to 2 (ambulatory and capable of all self-care but unable to carry out

any work activities. Up and about more than 50% of waking hours), measured within 72 hours before the start of treatment.

- 6. Predicted life expectancy of  $\geq$  3 months.
- 7. Adequate renal function [creatinine  $\leq$  1.5 times ULN (upper limit of normal)] or GFR of  $\geq$  50mL/min.
- 8. Adequate hepatic function [total bilirubin  $\leq 1.5 \times \text{UNL}$ ; AST (aspartate transaminase) or ALT (alanine transaminase)  $\leq 3 \times \text{UNL}$  or  $\leq 5 \times \text{UNL}$  if due to liver involvement by tumor].
- 9. Adequate cardiac function,  $\geq$  institutional lower limit of normal, e.g., left ventricular ejection fraction (LVEF) of  $\geq$  50% as assessed by multi-gated acquisition (MUGA) or ultrasound/echocardiography (ECHO); corrected QT interval (QTc) < 470 ms.
- 10. Contraception:
  - For women: Negative pregnancy test for females of child-bearing potential; must be surgically sterile, postmenopausal (defined as no menstrual cycle for at least 12 consecutive months), or compliant with an acceptable contraceptive regimen (oral contraceptives, condom with spermicide etc.) during and for 3 months after the treatment period. Abstinence is not considered an adequate contraceptive regimen.

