# 5.1 STUDY PATIENT NUMBER

In Part 1, up to approximately 20 patients are expected to be enrolled.

In Part 2 of the study, up to approximately 40 patients with measurable disease will be enrolled:

- Group 1: patients with RAS mutant positive AML or MDS; n (evaluable)  $\leq 20$
- Group 2: patients with RAS mutant negative AML or MDS; n (evaluable  $\leq 20$

# 5.2 DESCRIPTION OF STUDY VISITS FOR PART 1

Procedures performed in the first cycle are specified in Table 6.3 (Part 1: Schedule of Assessments and Procedures). Patients receiving multiple cycles of treatment will not have blood drawn for PK and PD measurements after Cycle 1 (Day 1 and Day 22) unless additional PK and PD data are deemed necessary after initial analysis.

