#### Reference: (2).

Please note that all other responses are collected as "Less than PR" within the eCRF.

AML – The response criteria for AML will be based on modified recommendation of the International Working Group (IWG) published in 2003 (1). Information regarding transfusion dependence will be noted as a visit assessment and space provided in the eCRF.

Table 6.2	Table 4 from IWG 2003 AML Response Criteria
-----------	---

Response	Peripheral Blood	Bone Marrow
CR	ANC > 1.0 x $10^9$ /L, Platelets $\ge 100 \times 10^9$ /L, independence from red cell and platelet transfusions over the past week	$\leq$ 5% blasts
CRp	ANC > 1.0 x $10^9$ /L, Platelets < 100 x $10^9$ /L, independence from red cell transfusions over the past week	$\leq$ 5% blasts
Cri	$ANC < 1.0 \text{ x } 10^9/L$	$\leq$ 5% blasts
PR	ANC > 1.0 x $10^{9}$ /L, Platelets $\ge 100 \text{ x } 10^{9}$ /L	Decrease of $\geq$ 50% in blasts to level of 5% to 25%

ANC = absolute neutrophil count; CR=complete remission; CRp=complete remission with incomplete platelet recovery; Cri=CR with incomplete blood count recovery; PR=partial remission. Reference (1).

Please note that all other responses are collected as "Less than PR" within the eCRF.

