Complete Response with Incomplete Blood Count Recovery (Cri)	ANC $< 1.0 \times 10^9/L$	≤ 5% blasts
Partial Remission (PR)	ANC $> 1.0 \times 10^9$ /L, Platelets $\ge 100 \times 10^9$ /L	Decrease of ≥ 50% in blasts to level of 5% to 25%
Less than Partial Remission*		

ANC = absolute neutrophil count

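### AML patients who enter with 5% or fewer marrow blasts are not clearly excluded, and can be recorded as CRp or CRi at the first marrow with no drug effect

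*Protocol*

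**What the plan says.** **Eligibility.** Criterion 3 asks for a diagnosis. Its AML branch opens with "Morphologically confirmed AML (except acute promyelocytic leukemia (APL" and continues, in the synopsis, with patients "who have failed to achieve CR or who have relapsed after prior therapy and are not candidates for potentially curative therapy". Protocol 4.3 has the same rule. Neither the inclusion list (4.3) nor the exclusion list (4.4) gives a marrow-blast threshold or a date for the morphological confirmation. Section 5.1 adds that in Part 2 "up to approximately 40 patients with measurable disease will be enrolled". That phrase is not defined for AML and does not appear in either list.

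**Response.** Protocol Table 6.2 and SAP Table 9.2 give CR, CRp and CRi their own rows. The protocol's key reads "CRp=complete remission with incomplete platelet recovery; Cri=CR with incomplete blood count recovery". All three rows require at most 5% marrow blasts. PR is the only AML row that requires a fall in blasts. Section 6.8 calls its tables a summary and says the detailed published criteria govern the analysis.

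**Use.** Protocol 10.1.2 gives the purpose of Part 2 as documenting some evidence of response. It quotes an 88% chance of one or more responses per group of 20 at a true rate of 10%. PFS and DOR are to be determined in patients achieving CR or CRp (protocol 3.1.1.2 and 10.3.6, SAP 2.3.2). Response in Part 2 is calculated on the mITT and PP populations (SAP 5.3 and 5.4).

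**The concern.** Not having achieved CR is not the same as having active leukemia in the marrow. Under the trial's own table, a patient left by the last therapy with few blasts but low platelets or neutrophils has not reached CR and so meets that part of criterion 3. The CRp and CRi rows describe a state and ask for no change from baseline. The same patient, unaltered, can meet the same row on treatment.

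What is at stake is the meaning of a recorded response. Part 2 has no control arm and looks for as little as one response per group. A remission that was present at entry would be credited to the drug. If it were a CRp, it could also add a duration to the DOR and PFS summaries that started before treatment.

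**Working it through.** **Step 1: can a patient enter and be recorded without changing?** Take an illustrative AML patient with 3% marrow blasts after the last therapy.

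| Values at screening, unchanged at Day 22 | CR achieved? | Blast minimum in 4.3 or 4.4? | Row met at Day 22 |
|---|---|---|---|
| ANC above 1.0, platelets below 100, a week free of red-cell transfusion | No | None | CRp |
| ANC below 1.0 | No | None | CRi |

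The first on-treatment marrow is at Cycle 1 Day 22 (Table 6.3, footnote k). The AML rows state no minimum duration, so one assessment is enough.

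**Step 2: is a baseline condition left out everywhere?** No. For MDS, marrow CR requires a reduction in blasts and hematological improvement is measured against baseline counts (Table 6.1, SAP Table 9.1). The hematologic DLT definitions exclude Grade 4 cytopenias already present at entry (protocol 3.1.4.2). The AML CR, CRp and CRi rows have no counterpart.

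**Step 3: the plan's own figure.** With n = 20 and a true rate of 10% (protocol 10.1.2), P(at least one response in a group) = 1 − 0.9^20 = 1 − 0.122 = 0.878. The stated 88% is reproduced, per group.

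**Step 4: size, on assumed inputs.** Let q be the share of a Part 2 group (AML and MDS together) entering in CRp or CRi, and s the share of those still there at Day 22. The documents give neither, so both are assumptions. With an inactive drug:

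P(at least one such record in 20) = 1 − (1 − q·s)^20

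| q | s = 1 | s = 0.5 |
|---|---|---|
| 1% | 1 − 0.99^20 = 0.182 | 1 − 0.995^20 = 0.095 |
| 2.5% | 1 − 0.975^20 = 0.397 | 1 − 0.9875^20 = 0.222 |
| 5% | 1 − 0.95^20 = 0.642 | 1 − 0.975^20 = 0.397 |

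The expected number per group is small: 20 × 0.01 = 0.2 patients at q = 1% and 20 × 0.05 = 1 at q = 5%, with s = 1. The probabilities are large only because the benchmark is a single response. If response requires more than 5% blasts at baseline, such patients cannot count, this probability is zero, and the 88% calculation is unchanged.

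**The case against.** A reader might infer that criterion 3 knowingly admits patients in remission and that they will be scored as responders. The documents do not support that.

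- The criterion starts from morphologically confirmed AML, which reads naturally as current disease. Section 5.1 points the same way for Part 2. Every Screening/Enrollment Form goes to the Medical Monitor before treatment (5.2.1, 5.2.2).
- Section 6.8 hands the analysis to the published criteria, which may contain a baseline condition.
- Neither document says which categories make a positive response. CRi is outside the PFS and DOR set, and a patient already in CRp does not naturally achieve it on treatment.
- No formal efficacy analysis is planned (protocol 10.3.6). Responses are tabulated by category and listed by patient (SAP 14.2 and 14.5), and the screening marrow is on record, so a careful reader could spot a carried-over remission.

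This limits the point without closing it. The morphological confirmation has no date or threshold and may refer to the original diagnosis. The measurable-disease phrase is undefined and missing from the list against which eligibility is checked. The Medical Monitor's review has no stated blast rule. The published criteria cannot be checked here, both documents say the AML version is modified without saying how, and the SAP reprints the table without the deferral. An undefined positive response leaves nothing that excludes these patients.

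The objection to the numbers stands in full: q and s are not in the documents. It is also tempting to note that a 10% share would return the protocol's own 88%. That match is automatic, since the same 10% goes into the same formula, and it says nothing about how likely such a share is.

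**Conclusion.** The gap is real but narrow. Eligibility sets no baseline blast minimum for AML, and the AML CR, CRp and CRi rows carry no baseline condition. A patient entering without CR but with at most 5% blasts is not clearly excluded and can be recorded as CRp or CRi with no drug effect. Entry of a CRp patient to the PFS and DOR set is possible, not certain. Relapsed AML with blasts above 5% is not affected.

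The number of such patients is unknown and probably small. The 18% to 64% range (10% to 40% with half persisting) rests wholly on assumed shares of 1% to 5% and shows only that a one-response benchmark is sensitive to a single patient. It is not an estimate of bias in this trial. The point is worth acting on because the mitigating text is undefined or cannot be checked, and the remedy is cheap.

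**What to change.** In SAP 9.2.2, count AML CR, CRp or CRi as a response, and as entry to the PFS and DOR set, only when marrow blasts on the screening sample were above 5%. Keep patients with 5% or fewer at baseline in the mITT denominator as non-responders, and list them with any change of category.

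Separately, reconcile the measurable-disease phrase in protocol 5.1 with the inclusion lists in 4.3 and the synopsis. The sponsor should supply the AML definition. The SAP change does not depend on it.

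The cost is one line and one listing. The screening marrow is already collected. The downside is that a genuine improvement from baseline CRi or CRp to CR would appear only in the listing. Requiring a better category than at screening would keep such cases. However, it would also count a patient whose platelets simply recover after earlier therapy, which is possible because exclusion 6 allows a washout shorter than 28 days. The blast condition is the safer choice.
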